2.1.2 Secondary objectives

To evaluate:

- Mean change of visual acuity by comparing change of BCVA in ETDRS letters between baseline and month 12
- Frequency of visits and injections, treatment free intervals and visit
- mean change of central subfield retinal thickness (CSRT) and foveal center point thickness from baseline will be evaluated by central reading center assessing OCT images
- change in DRS retinopathy scale evaluated by central reading center scoring fundus photography
- Influence of relevant HbA1c-, blood pressure and blood lipid levels changes on primary objective (ANCOVA Analysis)

3 Investigational plan

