## 1.2 Study objectives and endpoints

The primary objective of this trial is to demonstrate that the mean average change from baseline of BCVA in Early Treatment of Diabetic Retinopathy Study (ETDRS) letters averaged over all post-baseline visits to month 12 in patients with DME treated with ranibizumab injections at the DI and in accordance with disease activity criteria is non-inferior to current standard of care (PRN).

The secondary objectives seek to evaluate:

- Mean change of BCVA in ETDRS letters from baseline to month 12
- Frequency of visits, injections and treatment free intervals (TFIs)
- Mean change of central subfield retinal thickness (CSRT) and foveal center point (FCP) thickness from baseline to month 12
- Change in Diabetic Retinopathy Scale (DRS) from baseline to month 12
- Influence of relevant glycosylated hemoglobin (HbA1c), blood pressure, and blood lipid levels changes on the primary objective

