Additional ANCOVA models for the primary outcome (visit-averaged change from baseline in BCVA from month 1 to EoT) will be performed with the following extra binary covariates (Yes, No):

- relevant changes of HbA1c (defined as any change of HbA1c (%) from baseline of  $> 1\%$ )
- relevant changes of systolic blood pressure (defined as any change of systolic blood pressure (mmHg) from baseline  $> 30$ )
- relevant changes of diastolic blood pressure (defined as any change of diastolic blood pressure (mmHg) from baseline  $> 20$ )
- relevant changes of cholesterol (defined as any change in cholesterol from baseline of (1) for female:  $\leq 2.38$  mmol/l; 92 mg/dl or  $\geq 6.06$  mmol/l; 234 mg/dl, (2) for male:  $\leq 2.12$  mmol/l; 82 mg/dl or  $\geq 4.97$  mmol/l; 192 mg/dl)
- relevant changes of HDL-cholesterol (defined as any change in HDL-cholesterol from baseline of  $\leq 1.04$  mmol/l; 40 mg/dl)
- relevant changes of LDL-cholesterol (defined as any change in LDL-cholesterol from baseline of  $\geq 3.38$  mmol/l; 130 mg/dl)
- relevant changes of triglycerides (defined as any change in triglycerides from baseline of  $\geq 1.71$  mmol/l; 150 mg/dl)

For each ANCOVA model, the LS (“adjusted”) means for each treatment arm and estimates of the difference (DI - PRN) will be given along with the respective two-sided, 95% CI together with two-sided p-values. In order to derive the final ANCOVA model, the following steps will be used:

[figure not shown]
1. The importance of the individual dependent variables on the primary outcome response variable will be testing using the primary ANCOVA model (see [Section 2.6.2](#) for details) for FAS (LOCF). Inclusion in the primary ANCOVA model when  $p < 0.2$ .
2. The backward stepwise regression procedure will be used to choose the optimal set of dependent variables from the set of statistically significant dependent variables tested in step 1. The significance level to stay in the ANCOVA model is  $p < 0.05$ .

Note: In case of inadequate results, further modification of the model may be required.

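### The HbA1c and blood-pressure covariates ignore the direction of change, which weakens, and can cancel, the influence that this secondary analysis is meant to estimate

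*SAP*

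**What the plan says.** Protocol 2.1.2 lists as a secondary objective the "Influence of relevant HbA1c-, blood pressure and blood lipid levels changes on primary objective (ANCOVA Analysis"), and SAP 1.2 repeats it. Protocol 9.5.1 makes relevant changes in HbA1c, blood pressure and lipids additional covariates in an ANCOVA of the primary outcome.

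SAP 2.8.2 supplies the coding. The models "will be performed with the following extra binary covariates (Yes, No"). Three of the definitions are:

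- "relevant changes of HbA1c (defined as any change of HbA1c (%) from baseline of" more than 1%);
- "relevant changes of systolic blood pressure (defined as any change of systolic blood pressure (mmHg) from baseline" by more than 30);
- "relevant changes of diastolic blood pressure (defined as any change of diastolic blood pressure (mmHg) from baseline" by more than 20).

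Selection has two steps: "Inclusion in the primary ANCOVA model when" p < 0.2, then backward elimination, where "The significance level to stay in the ANCOVA model is" p < 0.05. Each model reports adjusted means and the DI minus PRN difference.

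Two other places describe the terms differently. SAP Table 5-3, footnote 2, keeps the relevant changes but calls them linear covariates. SAP 5.2.1 says that linear covariates such as HbA1c or blood pressure might be included, and mentions neither relevant changes nor Yes/No coding. The lipid covariates are defined in another way and are outside this point.

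**The concern.** A Yes/No indicator without a sign gives a patient whose HbA1c falls by 1.5 points the same value as one whose HbA1c rises by 1.5 points. If better control goes with better vision and worse control with worse vision, the two groups pull the Yes mean in opposite directions. The coefficient then measures the imbalance between rises and falls more than the effect of the change. If the sponsor meant rises only, large falls are merged with no change, which also dilutes the contrast.

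At stake is one of the five secondary objectives in SAP 1.2. A covariate that is weak because of its coding is more likely to fail the two selection steps, and the report could then be taken to show that systemic control has little influence.

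**Working it through.** **Which reading the text supports.** Where the documents mean one direction they say increase or decrease (Protocol Appendix 1; SAP Table 2-4). Protocol Appendix 1 uses the same 30 and 20 mmHg cut-offs for both rises and falls of blood pressure. SAP 2.1.1 also uses change without direction when it defines unstable BCVA and retinal thickness. The natural reading is therefore a change in either direction. The SAP never writes an absolute value, so a rise-only reading stays possible, and both are checked.

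**The plan's own figure.** The plan gives no power for this analysis. Its one formal sample size reproduces: 2(1.960 + 1.282)² × 10² / 4² = 131.4, so 132 per arm by normal approximation and 133 by the exact t-test, as stated. Only the SD of 10 letters is carried over.

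**Inputs.** From the SAP: 135 patients enrolled, SD 10 letters (used as the residual SD), thresholds, p < 0.2 and p < 0.05. Assumed, because the documents give no values: HbA1c change normal with SD 1 point, mean 0 to -1.0; BCVA outcome = -2 × change + error. One covariate at a time, without center or baseline BCVA.

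**By hand, mean change 0.**
- Signed continuous: SE of slope = 10/√135 = 0.861; 2/0.861 = 2.32; power = Φ(2.32 - 1.96) = 64%.
- Either direction: 15.9% rise and 15.9% fall by more than 1 point. The mean change is 0 in both Yes and No, so the expected difference is 0 letters and power equals the error rate.
- Rise only: mean change 1.525 in Yes and -0.288 in No; difference -2 × 1.813 = -3.63 letters; SE 2.38; power = Φ(1.52 - 1.96) = 33%.

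**By hand, mean change -1.0, either direction.** 2.3% rise and 50% fall beyond the threshold. Mean change is -1.660 in Yes and -0.277 in No; difference -2 × (-1.383) = 2.77 letters. SE = 10.1 × √(1/70.6 + 1/64.4) = 1.74. Power = Φ(1.59 - 1.96) = 36% at 5% and Φ(1.59 - 1.28) = 62% at 20%.

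**Simulation of the same model (20,000 data sets each), power at 5%:**

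| Mean change | Signed continuous | Either direction > 1 | Rise > 1 | -1/0/+1 score (1 df) | Three-level factor (2 df) |
|---|---|---|---|---|---|
| 0 | 62.3% | 5.4% | 31.4% | 49.6% | 39.1% |
| -0.3 | 62.5% | 10.9% | 25.7% | 49.7% | 39.6% |
| -0.6 | 62.9% | 22.5% | 19.2% | 49.8% | 39.4% |
| -1.0 | 62.7% | 34.7% | 12.3% | 47.0% | 37.7% |

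Repeat runs moved these by one or two points. At the p < 0.2 screen the either-direction coding passes in 20.3%, 30.2%, 47.6% and 61.5% of data sets. With slope -1.5 at mean 0, power is 41% (signed), 5% (either direction) and 21% (rise only).

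**Other assumptions (total SD 10), power at 5%.**
- HbA1c, SD of change 1.2, slope -2: either direction 5.4% at mean 0 and 38.8% at mean -1.0, against 80 to 81% signed and 67 to 70% for the score. At slope -4 and mean 0 the either-direction coding is still at 5.9%.
- Systolic, SD 20, -0.15 letter per mmHg: either direction 7.6% at mean 0 and 40.2% at mean -10, against 70 to 73% for the score.
- Diastolic, SD 12, -0.25 letter per mmHg: either direction 8.3% at mean 0 and 39.2% at mean -6, against 61 to 66% for the score.

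**How often Yes occurs, systolic.** With mean change 0 and SD 15 to 20, a rise above 30 mmHg has probability 1 - Φ(2) to 1 - Φ(1.5), or 2.3 to 6.7% (about 3 to 9 of 135). Either direction doubles this to about 5 to 13%.

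**The case against.** The objective speaks of the influence of relevant changes. It does not say that direction is the question, and part of the analysis is the adjusted DI minus PRN difference, which is not shown here to move. A clinical threshold is a legitimate choice, and for blood pressure Appendix 1 does treat large falls as notable too. SAP 5.2.1 can be read as already allowing continuous terms, and 2.8.2 allows the model to be modified. The safety sections report signed changes and shift tables. The analysis is interpreted descriptively. The simulations use assumed slopes and SDs, the number enrolled instead of the number with complete data, and no center or baseline term.

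Much of this stands and limits the point. A reader might infer that the objective will probably be reported as showing no influence, or that selection is bound to remove these covariates. The documents do not support either: full cancellation needs a monotone effect and balanced rises and falls, and neither is documented. With a mean change of -1.0 the covariate passes the first screen in about 62% of data sets. Even signed change has only about 63% power, so a null result could also come from sample size. A rise-only coding does not lose direction entirely.

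What the objection does not remove is that SAP 2.8.2 leaves the direction open. A 0/1 variable entered linearly, as footnote 2 would have it, is the same model. The safety tables do not link direction to BCVA, and a model change after seeing results is weaker than a prespecified coding.

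**Conclusion.** The concern holds in a limited form. The coding in SAP 2.8.2 merges rises with falls or, on the other reading, falls with stability, so a monotone influence on BCVA is underestimated. Under the main assumptions, power at 5% is 5 to 6% with balanced changes and about 35% at a mean change of -1.0, against about 63% for signed continuous change. The -1/0/+1 score gives 47 to 50%. A three-level factor on two degrees of freedom gives 38 to 39%, a clear gain when changes are balanced but little at a mean of -1.0, although it still shows the direction.

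The size of the loss depends on the mean, spread and slope, none of which the documents give. The primary non-inferiority result is untouched. This is a worthwhile, inexpensive correction to a descriptive secondary analysis.

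**What to change.** In SAP 2.8.2, enter HbA1c, systolic and diastolic change as signed continuous covariates. If the protocol's notion of a relevant change is to be kept, use three levels instead (fall beyond threshold, within, rise beyond threshold) and say whether they enter as an ordered score or as a factor.

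State the time point. Protocol Table 6-1 lists post-baseline HbA1c in the PRN arm at months 3, 8 and 12, so a patient could qualify in both directions if any visit counts. Blood pressure is scheduled after baseline only at the end-of-treatment and final visits (Protocol 6.5.2).

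Bring SAP 2.8.2, footnote 2 of Table 5-3 and the ANCOVA text in 5.2.1 to one description. Plain continuous change departs from Protocol 9.5.1, so record it in SAP section 4, which now states that nothing was changed.

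The cost is SAP wording before database lock, on data already collected. The continuous form assumes rough linearity, which a descriptive fall/within/rise table would let readers inspect. The three-level factor costs one extra degree of freedom per covariate.

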### 2.8.3 **Handling of missing values/censoring/discontinuations**

For certain secondary endpoints where specified, the analysis will follow a LOCF approach (see [Section 2.6.3](#) for details).

Otherwise the analysis will follow FAS as observed approach. Thus no imputation for missing values will be performed.

## 2.9 **Safety analyses**

Safety parameters will include AEs, intraocular pressure (IOP), vital signs, and laboratory results. All safety analyses will be performed using the Safety Set. Patients will be analyzed according to treatment received. No missing data will be imputed for safety analyses.

### 2.9.1 **Adverse events**

AEs will be deemed treatment emergent if the onset date is on or after the date of first treatment with investigational drug. Any AEs recorded prior to the start of investigational drug will be listed together with all other AEs. Only TEAEs will be summarized. If any event has an incomplete onset date, this will be handled as described in the [Appendix 5.1.1](#).

The period for observing TEAEs for the study eye begins at the first administration of study treatment. This safety observation period (days) for the study is defined as: (date of last administration of investigational study treatment - date of first administration of study drug) + 31 (i.e. 30 days after last administration of investigational study treatment).

TEAEs will be presented for both eyes in addition to the study eye and fellow (untreated) eye separately. AEs will be summarized by presenting for each treatment arm and total the number and percentage of patients having any AE (patient counts). Note: The overall TEAE summary table will in addition include the number of AEs within each category (event counts). AEs will be analyzed separately for ocular and non-ocular AEs (according to the

investigator's response to site on the AE eCRF form). Patients who experienced multiple AEs for a PT will be counted once, similarly for patients with multiple AEs per SOC. The SOCs will be presented in alphabetical order. PTs will be ordered within each SOC for both treatment arms and total by decreasing incidence in the total group.

Ocular AEs will be presented separately for the study eye, fellow eye and both eyes. Ocular AEs that were recorded in both eyes will be reported for both eyes and additionally separately for each eye.

AEs that were suspected to be related to study drug or procedures based on the investigator's decision will be summarized. The maximum severity of all TEAEs during the study (safety observation period) will be summarized. Summary tables will also be presented for the subset of AEs suspected to be treatment related.

Deaths, serious adverse events (SAEs), and AEs leading to discontinuation of investigational study treatment will be listed separately and, if appropriate, summarized by primary SOC and PT. To summarize, the following AE summaries will be presented for non-ocular, study eye, and fellow eye AEs (if applicable) for the TEAE safety observation period:

- all AEs
- AEs by maximum severity
- SAEs
- AEs leading to investigational study treatment discontinuation
- AEs suspected to be related to investigational study treatment
- AEs suspected to be related to ocular injection
- AEs suspected to be related to investigational study treatment and/ or ocular injection.

All information pertaining to AEs noted during the study (including AEs during the screening period, TEAEs and AEs during the post-treatment period) will be listed by patient, detailing AE (e.g., verbatim given by the investigator as well as the SOC and PT according to MedDRA), date of starting and ending, severity, suspected relationship (by the investigator) to the study drug/ ocular injection, and eye (for ocular events). The AE onset will also be shown relative (in number of days) to the day of (first) initial study treatment.

For the legal requirements of ClinicalTrials.gov and EudraCT, two required tables on TEAEs which are not serious adverse events with an incidence greater than 5% and on treatment emergent SAEs and SAEs suspected to be related to study treatment will be provided by SOC and PT on the Safety Set.

If for a same patient, several consecutive AEs (irrespective of study treatment causality, seriousness and severity) occurred with the same SOC and PT:

- a single occurrence will be counted if there is  $\leq 1$  day gap between the end date of the preceding AE and the start date of the consecutive AE
- more than one occurrence will be counted if there is  $> 1$  day gap between the end date of the preceding AE and the start date of the consecutive AE

For occurrence, the presence of at least one SAE/ SAE suspected to be related to study treatment/ non SAE has to be checked in a block e.g., among AE's in a  $\leq 1$  day gap block, if at least one SAE is occurring, then one occurrence is calculated for that SAE.

The number of deaths resulting from SAEs suspected to be related to study treatment and SAEs irrespective of study treatment relationship will be provided by SOC and PT.

The following AE by-patient listings will also be provided:

- deaths
- SAEs
- AEs leading to investigational study treatment discontinuation
- AEs related to ocular/ systemic risks
  - Ocular/ systemic risks will be defined based on important identified and potential risks as outlined in the most recent version of the Risk Management Plan (RMP)
- all AEs
- AEs suspected to be related to investigational study treatment and/ or ocular injection.

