5.5.11 Study completion and post-study treatment

Patients will be discharged from the study after visit 14 (month 12).

The investigator must provide follow-up medical care for all patients who are prematurely withdrawn from the study, or must refer them for appropriate ongoing care. This care might include treatments as recommended in current guidelines (Stellungnahme der Deutschen

Ophthalmologischen Gesellschaft, der Retinologischen Gesellschaft und des Berufsverbandes der Augenärzte Deutschlands, 2013, Bandello 2012).

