9.5.2 Safety variables

Safety parameters will include adverse events, the results of ophthalmic examinations, IOP, vital signs, and laboratory results.

All safety analyses will be performed using the Safety Set.

Adverse Events

Adverse events will be deemed treatment emergent if the onset date is on or after the date of first treatment with investigational drug. Any adverse events recorded prior to the start of investigational drug will be listed together with all other adverse events. Only treatment emergent adverse events will be summarized.

Adverse events will be summarized by presenting for each treatment group the number and percentage of patients having any adverse event, having an eye-related adverse event, having an adverse event in each primary system organ class and having each individual adverse event based on the preferred term. Patients who experienced multiple adverse events for a preferred term will be counted once, similarly for patients with multiple adverse events per system organ class. Eye-related adverse events (as identified by the investigator) will be presented separate for the study eye and the fellow eye. Ocular AEs that were recorded in both eyes will be reported for each eye separately.

All other information collected (e.g., severity or relationship to study treatment) will be tabulated and listed as appropriate. Summary tables will also be presented for the subset of adverse events suspected to be treatment related.

[figure not shown]
Deaths, serious adverse events, and adverse events leading to discontinuation of study treatment will be listed separately and, if appropriate, summarized by primary system organ class and preferred term.

Vital signs and IOP

Vital signs will be summarized by presenting shift tables using extended normal ranges with thresholds representing clinical relevant abnormality (Appendix 1) and by presenting descriptive statistics of raw data and change from baseline. Values outside the extended normal range will be listed by patient and treatment group and flagged in data listings. IOP measurements will be presented descriptively (absolute values and change from baseline).

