### 1.1 Study design

This is a 12-months, phase IV, randomized, parallel-group, visual acuity (VA) assessor-masked, multi-center, interventional study to assess the efficacy and safety of Discretion of the investigator (DI) vs. Pro re nata (PRN) (as needed) regimens of 0.5 mg ranibizumab intravitreal (IVT) injections for adult patients with Type I or Type II diabetes mellitus and visual impairment (VI) due to diabetic macular edema (DME).

A total of 300 patients from approximately 45 centers across Germany were initially planned to be randomized and assigned into one of the treatment arms in a ratio of 1:1. After new and relevant scientific evidence regarding treatment patterns with ranibizumab was published, recruitment to the study was revised and reduced to a total of 135 patients randomized and assigned in a 1:1 ratio to the treatment arms:

- Arm 1 (discretion of the investigator, DI): Investigational, RFB002, 10 mg/ml
- Arm 2 (pro re nata, PRN): Standard of Care, RFB002, 10 mg/ml

The study duration will be up to 13 months (the period of one month is considered to be equal 30 days):

[figure not shown]
- Screening period: to occur between day -28 and day -3
- Baseline period: to occur between day -2 and day 1
- Treatment period: from baseline (visit 2) to month 11
- Follow-up period: from month 11 to month 12

For patients randomized to the PRN treatment arm the treatment period is from baseline (date of first administration of study treatment) to month 11 with follow-up period up to month 12, whereas for patients randomized to the DI treatment arm the treatment period end date depends on the patient's individual schedule which may occur at the month 11 visit, but not later.

For patients with last injection at the month 11 visit, the follow-up period ends at the month 12 visit; for patients with last injection on or before the month 10.5 visit, the follow-up period ends on or before the month 11.5 visit.

No interim analyses will be performed.

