## 4 Change to protocol specified analyses

No change from protocol specified analysis was made.

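### SAP 2.9.1 confines its main AE and SAE tables to 30 days after the last ranibizumab injection, narrowing protocol 9.5.2 without declaring it in SAP section 4

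*SAP*

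**What the plan says.** Protocol 9.5.2 fixes only a start: "Adverse events will be deemed treatment emergent if the onset date is on or after the date of first treatment with investigational drug". It adds that treatment-emergent events are the ones summarised, and it names no end.

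SAP 2.9.1 opens with the same rule: "AEs will be deemed treatment emergent if the onset date is on or after the date of first treatment with investigational drug". It then defines a period for observing these events, in days, as "date of last administration of investigational study treatment - date of first administration of study drug) + 31", explained as ending 30 days after the last investigational treatment. SAP 2.1.1 identifies the investigational treatment as ranibizumab, so laser does not extend the period.

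The maximum-severity summary is tied to that period. So are the bulleted tables (all AEs, severity, SAEs, discontinuations, related events): "the following AE summaries will be presented for non-ocular, study eye, and fellow eye AEs (if applicable) for the TEAE safety observation period". The listing covers everything, and its wording treats later events as a separate group: "including AEs during the screening period, TEAEs and AEs during the post-treatment period) will be listed by patient". The ClinicalTrials.gov and EudraCT tables and the death counts carry no stated window.

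SAP section 4 reads: "No change from protocol specified analysis was made".

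**The concern.** The trial compares two strategies for deciding when to inject, and withholding injections from a stable eye is part of both. SAP 2.1.1 runs the maintenance phase to the end-of-study visit. Protocol 5.5.3.3.1 requires monthly monitoring in the PRN arm and monitoring at least every 3 months in the DI arm. Protocol 5.5.11 discharges patients after visit 14 at month 12. A patient who needs no further injection is therefore still on the assigned strategy and still being observed.

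A window that closes 30 days after the last injection drops part of that observed time from the main by-arm tables. Its length is set by something that happens after randomisation. Events that protocol 9.5.2 would summarise would appear only in listings, and a reader who trusts SAP section 4 would not know that the tables cover less than the protocol promised. If the registry and death tables were programmed on the open-ended definition, their counts need not agree with the bulleted tables.

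**Working it through.** **Inputs.** A month is 30 days (SAP 1.1). Baseline, the first administration, is study day 1 (SAP 2.1.1). The target day for month m is 30m, and month 12 is day 360 (SAP Table 2-3).

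**The SAP's own figure.** For a last injection on day 30m, the period length is (30m − 1) + 31 = 30m + 30 days. Counting from day 1, the last covered day is also 30m + 30, which is 30 days after the injection. The formula and its explanation agree.

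**Time outside the period.** Days to month 12 not covered = 360 − (30m + 30) = 330 − 30m.

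| Last injection | Study day | Period ends | Days outside, of 360 |
|---|---|---|---|
| Month 3 | 90 | 120 | 240 (67%) |
| Month 4 | 120 | 150 | 210 (58%) |
| Month 6 | 180 | 210 | 150 (42%) |
| Month 8 | 240 | 270 | 90 (25%) |
| Month 10 | 300 | 330 | 30 (8%) |
| Month 11 | 330 | 360 | 0 |

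The two rules coincide up to day 360 only when the last injection is at about month 11. For a last injection at month 4, an event starting on any day from 151 to 360 is treatment-emergent under protocol 9.5.2 but lies outside the bulleted tables. Under the protocol definition the uncovered time is 0 in every row.

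**Are the later events in the data?** Protocol 7.2 collects SAEs until 30 days after the last dose or last visit, whichever is later. With a last visit on day 360 that is day 360 + 30 = 390, so for the month-4 patient SAEs are collected for 390 − 150 = 240 days beyond the SAP period. Non-serious events reported after the observation period go to source documents only (protocol 7.1). AEs and SAEs therefore have different collection ends, and any common table window has to name its own.

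**Does follow-up really run to month 12?** SAP 1.1 says that "for patients with last injection on or before the month 10.5 visit, the follow-up period ends on or before the month 11.5 visit". That gives a latest date for this group. If it were read as ending follow-up 30 days after the last injection, nothing would fall outside the window. That reading does not fit protocol 5.5.11 or the maintenance phase in SAP 2.1.1, so the sentence needs reconciling.

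**The case against.** The strongest reply is that SAP 2.9.1 does not hold two rival definitions. Its opening sentence gives a start and the next paragraph supplies the end. The severity summary, the bulleted tables and the listing text all use the bounded period, so the intent for those tables is clear. This stands: a reader might infer that the section flatly contradicts itself and that a programmer could choose either rule for the bulleted tables, but the text states their window. What remains is that the window narrows what protocol 9.5.2 summarises.

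Second, protocol section 9 leaves technical details to the SAP, and an end date might be one. That would be fair if the end date left the summarised events unchanged. Here it removes on-study events from the main tables, so it belongs in SAP section 4. The registry tables might be said to inherit the window through the term TEAE, but the text does not say so.

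Third, a window of dose plus 30 days is a familiar convention, the analysis is exploratory, and all AEs, SAEs and deaths are listed by patient. No data are lost and the tables could be rerun. This limits the seriousness of the point. It does not make the convention suit a comparison of strategies that include not injecting.

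**Conclusion.** The point holds as an undeclared narrowing of the protocol's safety summary. It should be fixed, but it does not threaten the trial. Its size can be stated only per patient: 210 days outside the window for a last injection at month 4, 90 for month 8 and 0 for month 11. These figures assume 30-day months and follow-up to day 360.

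Two further inferences are tempting, and the documents support neither.

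- **A trial-wide share of follow-up lost.** The amendment summary in the protocol reports that 19.5% of patients in earlier PRN arms needed no injection from month 5 to 12. A reader might compute 0.195 × 210 / 360 = 11.4% and call it a minimum. The 19.5% comes from a post-hoc analysis of other studies. The DI arm here also allows treat-and-extend or fixed dosing, which could move last injections later. The number of patients affected in this trial is not derivable.
- **Bias towards one arm.** The timing of the last injection could differ between DI and PRN, but the documents give no event rates, no distribution of last injections and no direction.

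**What to change.** In SAP 2.9.1, apply the protocol 9.5.2 definition to all AE, SAE, death and registry tables, with no cut-off set by the last injection alone and with one stated end. One workable end is the last study visit or 30 days after the last injection, whichever is later. List or tabulate separately the SAEs reported after the last visit under protocol 7.2. If the view limited to 30 days after the last injection is wanted, keep it as a supplementary table and declare it in SAP section 4. Reconcile the follow-up sentence in SAP 1.1 with protocol 5.5.11 and SAP 2.1.1.

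A separate, minor item: SAP 2.9.2 counts and flags baseline IOP of 25 mmHg or more, yet presents the count by visit, before and after injection. A baseline value does not change by visit, so the word baseline is probably a slip. It should read IOP of 25 mmHg or more at each visit.

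The cost is SAP wording and one flag in the AE dataset. The data are already collected, and SAP 2.5.1.1 already derives an observation period to the last visit. The effect on reported AE percentages cannot be stated, because the documents give no event rates.
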